#### **13.4.3.1 Primary Analysis**

The primary efficacy endpoint of this study is the change from Baseline to Week 12 in the WOMAC pain score, and key secondary endpoints are the change from Baseline to Week 12 in the WOMAC physical function and WOMAC stiffness. The primary analysis set is the ITT. The comparison of interest is: HP-5000 versus placebo.

The fixed-sequence procedure will be applied for primary and key secondary endpoints of this study, where the order in which the hypotheses are tested is pre-specified as following: (1) WOMAC pain, (2) WOMAC physical function, and (3) WOMAC stiffness. Testing begins with the first hypothesis ( $H_1$ ) about WOMAC pain, and each test is carried out as long as significant results with level of significance  $\alpha=0.05$  are observed in all preceding tests. The fixed-sequence procedure controls the family-wise error rate because, for each hypothesis, testing is conditional upon rejecting all hypotheses earlier in the sequence.

All statistical tests of hypotheses in this trial will be 2-sided with a Type I Error rate of 0.05.

The estimand in the primary analysis for efficacy is the difference between treatment groups (HP-5000 vs. placebo) in the change from Baseline to Week 12 in WOMAC pain score in all randomized subjects from the ITT population and taking into account intercurrent events using the composite strategy. The study treatment discontinuation due to reasons related to study treatment (e.g. adverse events (AE), lack of efficacy (LOE), etc.), rescue medication use within 24 hours of WOMAC pain assessment, removal/detachment of the patch for more than 24 hours before WOMAC pain assessment are defined as intercurrent events.

Composite strategy will be applied to the stratum of subjects experiencing intercurrent events.

For the intercurrent events of study treatment discontinuation due to reasons related to study treatment (e.g. adverse events (AE), lack of efficacy (LOE), etc.), the obtained WOMAC pain score will be addressed in the analysis by expecting the long-term benefit from the treatment for that patient to be zero from the time of intercurrent event. For the other intercurrent events including rescue medication use within 24 hours of WOMAC assessment and removal/detachment of study patch for more than 24 hours before WOMAC assessment, the obtained WOMAC pain score will not be included in the analysis.

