The primary efficacy variable, change from Baseline to Week 12 in the WOMAC pain score, will be analyzed using a mixed model repeated measures (MMRM) analysis. The MMRM model will include change from Baseline in WOMAC pain score as the repeated dependent variable, with treatment (HP-5000 and placebo), visit, treatment-by-visit interaction, and the Baseline WOMAC pain score as covariates. An unstructured covariance matrix will be assumed. If the unstructured covariance matrix fails to converge, a series of other covariance structures will be tested for use.

Other sensitivity analyses will be performed on the primary endpoint to assess the robustness of the results based on the model used for primary analysis as described below.

The use of MMRM inherently implies that the treatment effect on the change from baseline in the WOMAC score will be similar for the patients who withdraw and for those who complete the study in their respective treatment groups, conditional on the outcomes observed prior to withdrawal (MAR [Missing at random] assumption). To assess the robustness of the MAR assumption, sensitivity analyses which utilize multiple imputations and a different assumption about unobserved outcomes will be performed, as detailed below.

A number of sensitivity analyses of the primary efficacy endpoint will be performed to assess the impact of assumptions about unobserved missing data patterns on the primary inferences after intercurrent events in the trial.

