#### Pattern-Mixture Model and Copy Reference Sensitivity Analyses of MMRM Approach:

Robustness of the primary results under MNAR (Missing not at random) mechanisms will be assessed using pattern-mixture model and copy reference imputation approaches. All sensitivity analyses will be based on the pattern mixture model using multiple imputation technique for the dropout reasons and their assumed pattern of missing data as follows:

- Not Study Treatment Related or Uncertain reason for withdrawn as MAR
- Study Treatment Related reason as MNAR

- a. Multiple Imputation: Pattern Mixture Model (PMM)

The missing data due to early discontinuations will be imputed assuming MNAR following the approach described in Permutt (2016). That approach will be implemented by imputing missing

data first under the MAR assumption in each treatment group using multiple imputation and then adding a pre-defined  $\Delta 1$  to each imputed value in the placebo group and adding a different pre-defined  $\Delta 2$  to each imputed value in the active treatment group, then varying  $\Delta 1$  and  $\Delta 2$  over an enclosure of a plausible range of values. As noted in the article by Permutt (2016), this is considered the most appropriate kind of sensitivity analysis for the missing data problem. Also, this imputation approach was documented on Page 89 of the NRC report (2010).

b. Multiple Imputation: Copy Reference (Placebo) Approach

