7.3 MISSING DATA

The total and subscale scores of any assessment with more than one item, will be derived from individual items. Any individual missing item in any scale will not be imputed. If one or more items are missing at a visit, then the associated total score or subscale score will be set to missing.

Missing WOMAC scores will be imputed and used in sensitivity analyses of the primary and key secondary efficacy as per [section 16.1.4](#) and [16.1.5](#).

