16.1.2 MISSING DATA METHODS FOR PRIMARY EFFICACY VARIABLE

The primary analysis method for evaluating the primary efficacy endpoint is the likelihood-based analysis of repeated measures, a mixed model with repeated measures (MMRM) under an assumption that the missing observations of change from baseline WOMAC pain score are missing at random. To assess the robustness of the MAR assumption, sensitivity analyses which utilize multiple imputations and different assumption about unobserved outcomes will be performed, as detailed in [Section 16.1.4](#).

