16.1.4 COMPOSITE STRATEGY ANALYSIS FOR PRIMARY EFFICACY

Composite strategy will be applied to the stratum of subjects experiencing intercurrent events.

For the intercurrent events of study treatment discontinuation due to reasons related to study treatment (AE, LOE, etc.), the obtained WOMAC pain score will be addressed in the analysis by expecting the long-term benefit from the treatment for that subject to be zero from the time of intercurrent event. For the other intercurrent events, rescue medication use within 24 hours of WOMAC assessment, removal/detachment of study patch for more than 24 hours before WOMAC assessment, the obtained WOMAC pain score will not be included in the analysis.

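### The zero-benefit rule for treatment-related discontinuation covers only obtained WOMAC scores and has no numerical value; visits missed afterwards fall to MAR, contrary to the composite estimand

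*SAP*

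**What the plan says.** The current text is protocol version 2.0, on which the SAP is based.

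- **Estimand.** Protocol 13.4.3.1 defines the primary estimand in all randomized subjects, "taking into account intercurrent events using the composite strategy". Three events are named: treatment-related discontinuation, rescue use within 24 hours of the WOMAC assessment, and patch off for more than 24 hours before it.
- **Discontinuation rule.** SAP 16.1.4 opens with "Composite strategy will be applied to the stratum of subjects experiencing intercurrent events". For treatment-related discontinuation, "the obtained WOMAC pain score will be addressed in the analysis by expecting the long-term benefit from the treatment for that subject to be zero", counted from the time of the event. Protocol 13.4.3.1 has the same rule, also limited to the obtained score.
- **Deletion rule.** The next sentence begins "For the other intercurrent events, rescue medication use within 24 hours of WOMAC assessment", adds patch-off, and removes those scores from the analysis.
- **Missing scores.** SAP 16.1.2 runs the primary MMRM "under an assumption that the missing observations of change from baseline WOMAC pain score are missing at random". Protocol 13.4.3.1 says the MMRM treats those who withdraw like completers of their own arm, "conditional on the outcomes observed prior to withdrawal".
- **Imputation.** SAP 7.3: "Missing WOMAC scores will be imputed and used in sensitivity analyses of the primary and key secondary efficacy". The protocol's sensitivity analyses list "Study Treatment Related reason as MNAR"; SAP 16.1.5 lists lack-of-efficacy, lack-of-efficacy plus AE, and all-dropout patterns.
- **Follow-up.** Protocol 8.2.3 encourages subjects who stop treatment to attend all visits without patches. Protocol 10.1.5 requires an Early Termination visit, with a WOMAC, from those who leave. SAP 6.3 windows that visit to a scheduled visit.

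**The concern.** A composite strategy makes the event itself part of the outcome, so the same event should lead to the same value whether or not the subject keeps attending. Here the rule acts on a score that was collected. Where none was collected, the general MMRM assumption applies, and it predicts the missing visit from earlier on-treatment scores. That is closer to a hypothetical value than to a composite one.

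Because zero benefit has no stated value, two programmers could also build different Week 12 datasets from the same data. WOMAC pain comes first in the fixed sequence, and SAP 16.2.2 carries the methods of 16.1.3 to 16.1.6 over to physical function and stiffness. All three confirmatory tests inherit the gap.

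**Working it through.** **The plan's own figure.** The documents give 80% power at two-sided 0.05, but effect size and N are redacted, so this cannot be reproduced. Nothing here contests it.

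**Subjects with a treatment-related stop, read literally**

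| Visit after the event | Primary-analysis handling | Source |
|---|---|---|
| Stays, score obtained | Zero benefit, value undefined | SAP 16.1.4 |
| Leaves, Early Termination WOMAC | Unclear whether post-event: the visit lists WOMAC before patch removal | Protocol 10.1.5, SAP 6.3 |
| Leaves, later visit missed | MAR | SAP 16.1.2, protocol 13.4.3.1 |

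**Size.** Rates, retention, N and the Week 12 means are not available, so every input below is assumed, including zero benefit = zero change from baseline. The assumed SD of 3.5 is compatible with SAP Appendix 3, which puts 1 SD below 4.

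Let p be an arm's rate of treatment-related discontinuation (A active, P placebo), s the share who stay, and m the Week 12 change that MAR implies for a leaver. Leaving aside the Early Termination score, the literal reading differs from zero-for-all by about

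gap = (1 − s) × (p_A·m_A − p_P·m_P).

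*Set A.* Week 12 change −5 active and −4 placebo; n per arm = 2 × (1.96 + 0.842)² × 3.5² / 1.0² = 192.3, so 193; discontinuation driven by poor earlier scores; 2,000 simulated trials per case; no Early Termination score. Leavers' m is about −3.0 (active) and −2.0 (placebo). With s = 0.5:

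- 10% v 10%: 0.5 × (−0.30 + 0.20) = −0.05. Simulated −0.96 v −0.91 for zero-for-all; power 77% v 72%.
- 15% v 10%: 0.5 × (−0.45 + 0.20) = −0.125. Simulated −0.86 v −0.73; power 63% v 51%.
- 10% v 15%: 0.5 × (−0.30 + 0.30) = 0. Simulated −1.03 v −1.04; power 79% v 80%.

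With 80% staying, the simulated gaps in size are 0.02, 0.05 and 0.00. With 20% staying they are 0.08, 0.21 and 0.01, the last in the other direction.

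*Set B.* Large-sample expectation (200,000 per arm) of an unstructured repeated-measures model without the baseline covariate; Week 12 change −6.0 v −5.0; correlation 0.6; AE stops at random, lack-of-efficacy stops concentrated in poor responders. Week 12 difference:

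| Discontinued, active / placebo | Zero for all | Half leave, MAR | All leave, MAR | Half leave, ET score set to 0 | All leave, ET score set to 0 |
|---|---|---|---|---|---|
| 9.8% / 9.7% | −0.91 | −0.96 | −1.01 | −0.94 | −0.97 |
| 12.7% / 5.9% | −0.54 | −0.76 | −1.02 | −0.65 | −0.80 |
| 19.3% / 9.7% | −0.32 | −0.62 | −1.01 | −0.47 | −0.67 |
| 7.8% / 14.5% | −1.05 | −1.03 | −1.00 | −1.05 | −1.04 |
| 12.7% / 12.7%, mainly AE on active, mainly lack of efficacy on placebo | −0.64 | −0.81 | −0.98 | −0.73 | −0.83 |

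In the second row, with half leaving, the gap is 0.76 − 0.54 = 0.22, or 0.65 − 0.54 = 0.11 if the Early Termination score is set to zero. The last row shows that equal overall rates do not remove the gap when the reasons differ: 0.81 − 0.64 = 0.17.

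**The case against.** The strongest reply is that SAP 16.1.4 works at subject level and runs forward in time: it applies to a stratum of subjects and sets benefit to zero from the event onward. On that reading it already covers missed visits, and SAP 16.1.2 states only the model's general assumption. This may well be the intent. But the rule's grammatical subject is the obtained score, and no step in the SAP assigns a value where there is none.

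Other replies carry part of the way:

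- **Leavers are not without data.** The Early Termination WOMAC can be one obtained score, and from day 74 it is windowed to Week 12. In set B, setting it to zero roughly halves the gap. Later missed visits remain MAR.
- **Few may leave.** Protocol 8.2.3 discourages withdrawal for AE or lack of efficacy, and classes loss to follow-up and unexplained withdrawal of consent as uncertain, outside the rule. How many stay is not given.
- **Zero benefit might mean placebo-like.** In set A with half staying, moving active leavers from −3.0 to −2.0 shifts the estimate by 0.10 × 0.5 × 1.0 = 0.05, or 0.15 × 0.5 × 1.0 = 0.075. That is smaller, and it shows why a definition is needed.
- **Sensitivity analyses reach this far.** In set A, zero-for-all corresponds to shifts of 2 (placebo) and 3 (active), inside the Appendix 3 range. The result would be visible, but those analyses do not define the primary estimate. Nor does the unadjusted analysis in SAP 16.1.6.

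A reader might also infer that stayers' scores are deleted, because subjects without patches also meet the patch-off definition. The documents do not support that: the word *other* in "For the other intercurrent events, rescue medication use within 24 hours of WOMAC assessment" implies that the discontinuation rule governs. It only needs saying outright.

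**Conclusion.** The point holds in this limited form: the primary rule for treatment-related discontinuation is undefined in value and silent on visits without a score. The only stated default for those visits is MAR, which conflicts with the composite estimand.

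A reader might infer that the sponsor means leavers to be MAR, that leavers never have a later score, or that the primary result is biased towards HP-5000 by a known amount. None of these follows. The forward-looking phrase leaves the intent open, the Early Termination visit may supply a score, and the documents give no rates.

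In the illustrations the gap is 0.1 point or less when the arms are alike in rates and reasons, and at most 0.05 in set A with 80% staying. It is about 0.1 to 0.3 points, and more in extreme cases, when active-arm discontinuation is higher and few stay; it then favours HP-5000. With more placebo discontinuation it is near zero or slightly reversed. These sizes rest on assumed means, rates and retention, and on zero benefit coded as zero change. The correction is cheap and should be made before unblinding.

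**What to change.** In SAP 16.1.4 and protocol 13.4.3.1:

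1. Define zero benefit numerically, for example change from baseline = 0, with the sponsor to confirm.
2. Apply it in the primary analysis at every scheduled visit after treatment-related discontinuation, whether or not a score was obtained.
3. State whether the Early Termination WOMAC counts as post-event.
4. State that this rule overrides the patch-off and rescue deletions.

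Minor points: describe the rescue and temporary patch-off deletions as hypothetical-type handling. Align the MNAR patterns in SAP 16.1.5 with Table B, which also assigns methods to those two events while the patterns name only dropout reasons. Correct the cross-references: SAP 2.4 places the composite strategy in 16.1.5, and SAP 16.1.2 places the sensitivity analyses in 16.1.4.

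The cost is wording and minor programming before unblinding, with no new data. The primary estimate may become less favourable to HP-5000.

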16.1.5 SENSITIVITY ANALYSIS OF PRIMARY EFFICACY VARIABLE

Further details of sensitivity analyses are provided in [Appendix 3](#).

Sensitivity analyses will be performed to assess the impact of assumptions about missing data patterns on the primary and key secondary efficacy inferences. Additional analysis due to intercurrent events occurring in the trial will be performed.

The intercurrent events are defined as:

1. Discontinuation due to reasons related to study treatment (e.g. AE, LOE, lack of compliance, deviation from protocol, etc.),
2. Rescue medication drug use within 24 hours of WOMAC pain assessment,

Noven Pharmaceuticals, Inc.

Protocol HP-5000-US-07

3. Removal/detachment of the patch for more than 24 hours before WOMAC pain assessment.

Table B provides details on how these intercurrent events will be used for the sensitivity analyses.

Table B: Sensitivity Analysis Methods for Intercurrent Events

Analysis	Endpoint	Methods for Intercurrent Events		
		Discontinuation related to Study Medication	Rescue Medication	Patch Removal/ Detachment
Primary Efficacy	Mean change in WOMAC pain score from baseline to Week 12	1. Pattern Mixture Model	1. Pattern Mixture Model	1. Pattern Mixture Model
		2. Copy Reference Model	2. Copy Reference Model	2. Copy Reference Model

Pattern-Mixture Model and Copy Reference Sensitivity Analyses of MMRM Approach:

Robustness of the primary results under MNAR (Missing not at random) mechanisms will be assessed using pattern-mixture model and copy reference imputation approaches. All sensitivity analyses will be based on the pattern mixture model using multiple imputation for the dropout reasons and their assumed pattern of missing data as follows:

- LOE as MNAR with other missing data as MAR
- LOE and AE as MNAR with other missing data as MAR
- Any reason (all dropout) as MNAR

a. Multiple Imputation: Pattern Mixture Model (PMM)

The missing data due to early discontinuation will be imputed assuming MNAR following the approach described in Permutt (2016)¹. That approach will be implemented by imputing missing data first under the MAR assumption in each treatment group using multiple imputation and then adding a pre-defined $\Delta 1$ to each imputed value in the placebo group and adding a different pre-defined $\Delta 2$ to each imputed value in the active treatment group, then varying $\Delta 1$ and $\Delta 2$ over an enclosure of a plausible range of values. As noted in the article by Permutt (2016)¹, this is considered the most appropriate kind of sensitivity analysis for the missing data problem. Also, this imputation approach was documented on Page 89 of the NRC report (2010)².

Noven Pharmaceuticals, Inc.

Protocol HP-5000-US-07

b. Multiple Imputation: Copy Reference (Placebo) Approach

This is placebo-based imputation for missing data which will be implemented assuming missing data from the placebo group as MAR and also as MNAR. This will be performed by first implementing placebo-based imputation for missing data in the active treatment group and the placebo group (as MAR). Then, an adjustment for MNAR in both treatment groups will be implemented by adding a common shift (Δ) to the imputed data, worsening the imputed data further, in both the placebo and the active treatment groups as described in Koch and Wienner (2016)³. This step is necessary because it is possible to have a lower treatment discontinuation rate in the active treatment group than in the placebo group and it is important to consider a MNAR approach in the placebo group in such a case. Using a similar argument as in the previous paragraph, the shift Δ will assume similar values to those of $\Delta 1$ (while the case of $\Delta=0$ represents the common copy placebo method, where missing data from placebo are considered as MAR).

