#### Pattern-Mixture Model and Copy Reference Sensitivity Analyses of MMRM Approach:

Robustness of the primary results under MNAR (Missing not at random) mechanisms will be assessed using pattern-mixture modeling and copy reference imputation approaches. All sensitivity analyses will be based on the pattern mixture model using multiple imputation technique for the dropout reasons and their assumed pattern of missing data as follows:

- Lack of efficacy (LOE) as MNAR with other missing data as MAR
- LOE, rescue medication and adverse events (AE) as MNAR with other missing data as MAR
- Any reason (all dropout) as MNAR

a. Multiple Imputation: Pattern Mixture Model (PMM)

The missing data due to early discontinuations will be imputed assuming MNAR following the approach described in Permutt (2016). That approach will be implemented by imputing missing data first under the MAR assumption in each treatment group using multiple imputation and then adding a pre-defined L1 to each imputed value in the placebo group and adding a different pre-defined L2 to each imputed value in the active treatment group, then varying L1 and L2 over an enclosure of a plausible range of values. As noted in the article by Permutt (2016), this is considered the most appropriate kind of sensitivity analysis for the missing data problem. Also, this imputation approach was documented on Page 89 of the NRC report (2010).

b. Multiple Imputation: Copy Reference (Placebo) Approach

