1. INTRODUCTION

This statistical analysis plan (SAP) is based on protocol version 2.0, dated 07 January 2021.

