3.3 CHANGES TO ANALYSIS FROM PROTOCOL

Not Applicable

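### SAP 16.1.5 does not list the protocol's missing-data pattern for the sensitivity analyses, and SAP 3.3 declares no change from the protocol

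*SAP*

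**What the plan says.** **Protocol (amended text), 13.4.3.1.** The pattern for the multiple-imputation sensitivity analyses has two lines: "Not Study Treatment Related or Uncertain reason for withdrawn as MAR" and "Study Treatment Related reason as MNAR". The classification comes from 8.2.3, where each discontinuation or withdrawal is recorded as treatment related, not treatment related or uncertain, with sub-reasons under each. At this point 13.4.3.1 leaves programming detail and SAS code to the SAP. It does not leave the choice of pattern.

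**SAP 16.1.5.** The list under the same heading reads "LOE as MNAR with other missing data as MAR", "LOE and AE as MNAR with other missing data as MAR" and "Any reason (all dropout) as MNAR". Appendix 3 gives the shifts and imputation steps and adds no further pattern. Earlier in 16.1.5, the first intercurrent event is treatment-related discontinuation, with non-compliance and protocol deviation among its examples. Table B assigns both the pattern-mixture and the copy-reference model to that event.

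**SAP 1 and 3.3.** "This statistical analysis plan (SAP) is based on protocol version 2.0, dated 07 January 2021". The section on changes from the protocol says only "Not Applicable".

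**The concern.** The sensitivity analyses test whether the primary result survives departures from MAR. The protocol fixed in advance which withdrawals are assumed to depart: those that the investigator attributes to treatment. If the SAP's list is programmed as it stands, that set is not among the runs. A reader of 3.3 would also be told that the executed analyses are the protocol's. At stake are the prespecified status of the robustness work on the primary endpoint and the accuracy of the SAP's statement about itself. The primary test is not at stake.

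**Working it through.** No sample-size or power figure enters, and the plan states no figure to reproduce. The check is a comparison of sets, followed by a comparison of texts.

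**Step 1: inputs.** Protocol 8.2.3 (amended) lists 4 treatment-related sub-reasons (LOE, AE, deviation, other), 7 not related (AE, prohibited medication, pregnancy, deviation, COVID-19, enrolled although ineligible, other) and 3 uncertain (lost to follow-up, consent withdrawn without reason, other). Total: 4 + 7 + 3 = 14.

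**Step 2: the MNAR set under each pattern.**

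| Pattern | MNAR sub-reasons | Omits from protocol set | Adds to protocol set |
|---|---|---|---|
| Protocol 13.4.3.1 | 4 of 14 | none | none |
| SAP: LOE | 1 of 14 | related AE, deviation, other | none |
| SAP: LOE and AE, any AE | 3 of 14 | related deviation, other | not-related AE |
| SAP: LOE and AE, related AE only | 2 of 14 | related deviation, other | none |
| SAP: all dropout | 14 of 14 | none | 10 (7 not related + 3 uncertain) |

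No SAP pattern equals the protocol's set under either reading of AE.

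**Step 3: is the mismatch an artefact of which protocol text is version 2.0?** The protocol file holds two full texts, and the version labels are not visible. The later one is taken as version 2.0 because only it has the composite estimand and the three reason categories that the SAP uses. The declaration in 3.3 fails against the other text as well: its second pattern is "LOE, rescue medication and adverse events (AE) as MNAR with other missing data as MAR", and the SAP's second pattern has no rescue medication. The close resemblance to that older list suggests incomplete updating.

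**Step 4: other differences that 3.3 does not list.**

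| Item | Protocol (amended) | SAP |
|---|---|---|
| Copy-reference shifts, WOMAC pain | 1, 2, 4, 8, 12, with 0 as the plain copy-placebo case (13.4.3.1) | 0, 1.3333, 2.6667, 4 (Appendix 3) |
| PGIC | MMRM (13.4.3.3) | logit model on responders (16.3.8) |
| Other secondary endpoints | handled like the primary analysis (13.4.3.3) | no adjustment for intercurrent events (16.3) |

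The largest pain shift thus falls from 12 to 4.

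**Step 5: what the size depends on.** With a common shift in both arms, the Week 12 difference (active minus placebo; positive is worse for HP-5000) moves by about shift × (active MNAR share − placebo MNAR share). The shift of 4 is the SAP's upper bound for pain. The shares below are assumptions chosen only to show the mechanism: LOE 4% active and 8% placebo; other treatment-related reasons 6% and 1%; not related or uncertain 4% and 9%.

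- LOE only: 4 × (0.04 − 0.08) = −0.16
- Protocol pattern: 4 × (0.10 − 0.09) = +0.04
- All dropout: 4 × (0.14 − 0.18) = −0.16

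With AE read as related AE, the LOE-and-AE pattern gives +0.04 if all the other related reasons are AEs and −0.16 if none are. If the reclassified share is the same in both arms, the common shift contributes nothing.

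**The case against.** **Table B.** The strongest counter-argument is that the SAP does direct MNAR methods at treatment-related discontinuation, protocol deviations included. This stands. A reader might infer from the list that the protocol's analysis would never be run, and Table B does not allow so categorical a statement. But Table B and the list a few lines below it say different things, and a programmer cannot tell which one governs.

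**The protocol case is spanned.** LOE lies within the treatment-related reasons, and those lie within all dropout, so the gap is an intermediate case and MNAR work is not absent. The nesting of reasons is correct. It does not guarantee that the results are nested: in Step 5 the protocol pattern falls outside the two outer ones.

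**The reading of AE.** A reader might infer that the LOE-and-AE pattern moves AEs coded as unrelated into MNAR. The SAP does not say so; elsewhere it cites AE as an example of a treatment-related reason. Under that reading only related deviation and other are misplaced.

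**The reason coding.** A reader might infer that the coding goes unused. It does not: it defines the discontinuation intercurrent event and its zero-benefit handling (SAP 16.1.4) and structures the disposition tables (SAP 9).

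**Some changes may be sensible.** PGIC has no baseline assessment in the schedule, so a change-from-baseline model could not be fitted as the protocol words it. And the protocol's likening of the secondary analyses to the primary one might cover only the model. Either is a reason to explain the change in 3.3, not to leave it out.

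**Conclusion.** The point holds as a mismatch between documents and an inaccurate declaration. The protocol's pattern is absent from the list in SAP 16.1.5, the list and Table B disagree, and 3.3 is wrong whichever protocol text is version 2.0. Only the sensitivity and secondary analyses are touched; the primary MMRM and the fixed-sequence alpha are unchanged.

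The magnitude cannot be given from the documents. It depends on how treatment-related deviation and other discontinuations split between arms, and the Step 5 figures are illustrations. A reader might multiply an assumed 3% or 6% of an arm by the 4-point shift and report 0.12 or 0.24 as the effect. Those would be shifts in one arm's mean, not in the treatment difference. With 3% in each arm the common shift cancels, and the pattern-mixture difference moves by at most 0.03 × |LS mean difference|, because the active shift exceeds the placebo shift by at most that difference.

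Nor does the text show that 3.3 conceals anything deliberately; it shows only that 3.3 is incomplete. Neither document ranks the sensitivity patterns, so nothing in them makes the protocol pattern the leading one.

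**What to change.** Before unblinding:

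1. Add the protocol pattern to the list in SAP 16.1.5 (treatment-related reasons MNAR; not related and uncertain MAR) and make the list and Table B agree.
2. Keep LOE, LOE and AE, and all dropout as additional analyses, and state whether AE there means any AE or only treatment-related AE.
3. Replace the entry in SAP 3.3 with a list of the actual differences from protocol version 2.0, each with a short reason: the MNAR patterns, the copy-reference shifts, the PGIC model, and the handling of intercurrent events in the other secondary endpoints.

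The cost is SAP wording and one more imputation run with the code already planned. The three reason categories are already recorded under protocol 8.2.3 and tabulated under SAP 9, so no new data are needed.
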